Patients with type 2 diabetes exhibit both deranged carbohydrate metabolism and a generalized inflammatory state. Inflammation in skeletal muscle, adipose tissue, and the liver contribute to insulin resistance, which in conjunction with decreased insulin secretion, account for the abnormalities in carbohydrate metabolism. Recent studies indicate that these metabolic and inflammatory changes are accompanied by the depletion of butyrate-producing and barrier permeability-regulating organisms within the gut microbiome.

In this exploratory intervention study, we intend to evaluate these issues within patients with early stage type 2 diabetes. This includes patients diagnosed but not exposed to anti-diabetic therapy and patients treated with the most commonly used initial treatment regimen, i.e. metformin and/or sulfonylurea. Two different medical food formulations will be tested: a formulation containing 2 butyrate-producing microbes and a third formulation consisting of the first formulation with approximately matching colony forming units (CFUs) of a third butyrate producer plus a barrier permeability-regulating strain, which has been associated with improved gut-epithelial barrier function in rodent studies. Subjects will receive their randomized formulation twice a day for 12 weeks, followed by a 4-week washout period.

C. Study Product Safety:

All bacteria contained in the study product formulations used in this study are commensal organisms that have been repeatedly documented to inhabit the human GI tract under normal circumstances. The organisms were grown under controlled conditions consistent with Good Manufacturing Practices (GMP) and employ no animal-derived products. All ingredients utilized during manufacturing were food grade and qualified as generally recognized as safe (GRAS). Each of the microbes have been characterized in detail (including whole genome sequencing) to ensure that mutations have not occurred. Each manufactured lot has also been tested with standard methods to ensure the absence of toxins, heavy metals, etc.

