All strains have also been tested *in vivo* in both a diet-induced obese mouse model and Sprague-Dawley rats. Each of these rodent models were dosed for 28 days at multiples ≥60 times (based on body weight) the amounts being administered in this study. In each study, safety was evaluated by clinical observation, routine chemistry, and hematology parameters, in addition to necropsy evaluation at study conclusion. In both studies no clinical, laboratory, or necropsy observations were observed that suggest adverse effects. In addition, a 5-person safety study was conducted with administration of 3 of the strains for 14 days using portions that were in excess of those proposed here without observing any adverse events or tolerability issues (See Portion Size

Whole Biome Study No: WB01-202_Ver 2_Amend 3 06/19/18

Page 6 of 45

Selection). For the other 2 strains, WB-STR-0001 and WB-STR-0008, this study will be the first exposure to humans.

D. Study Design:

This is a balanced, parallel-arm, double-blind, placebo-controlled study with the following 3-treatment arms:

- 1. Placebo (WBF-0009: excipients only)
- 2. WBF-0010 (two butyrate-producing strains)
- 3. WBF-0011 (WBF-0010 + an additional butyrate-producing strain + a barrier permeability-regulating strain)

The study is designed to test the hypothesis that oral administration of encapsulated formulations of the study products is safe and well-tolerated and yields beneficial metabolic and/or anti-inflammatory effects following administration for 12 weeks.

Primary Endpoint:

The primary endpoints for this exploratory study is the assessment of safety and tolerability, as assessed by adverse events; the efficacy endpoint is the change from baseline to Week 12 in the area under the glucose curve (ΔAUC_{glucose (0-180)}) during a standardized 3-hour meal tolerance test (MTT); and the primary inflammatory endpoint is the change from baseline to Week 12 in c-reactive protein (CRP).

Secondary Endpoints:

- 1. Assessment of change in the area under the insulin curve ($\Delta AUC_{insulin}$) from baseline to Week 12 during standardized meal tolerance test
- 2. Assessment of change in fasting glucose from baseline to Weeks 4, 12, and 16
- 3. Assessment of change in fasting insulin from baseline to Weeks 4, 12, and 16
- 4. Change in hemoglobin A1c from baseline to Weeks 4 and 12
- 5. Change in inflammatory markers from baseline to Weeks 4 and 12:
 - a. C-reactive protein (CRP)
 - b. IL-6
 - c. TNF-α

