Note: "Fasting Lipid Panel" includes fasting total cholesterol, TGs, LDL cholesterol, and HDL cholesterol; "Inflammatory Markers" include CRP, IL-6, IL-10, TNF- α , and TGF- β at Visit 1 (Day 0) and Visit 7 (Week 12); at Visit 3 (Week 4), only CRP, IL-6, and TNF- α are collected.

G. Duration:

The total duration of a subject's participation will be approximately 18 weeks, including the screening visit occurring 7 to 14 days prior to the baseline visit at Day 0. At the baseline visit, collection of baseline measures, randomization, and initiation of study product consumption will occur. Following the initiation of study product, active participation will extend through Week 16 (See **Appendix 1** for a display of study procedures by study visit).

H. Number of Subjects:

It is anticipated that approximately 90 subjects will be screened with \sim 75 subjects randomized to yield \sim 60 subjects completing the study (\sim 20 subjects/arm). All subjects will have been diagnosed with type 2 diabetes and currently treated with diet and exercise alone or in combination with metformin and/or sulfonylurea.

Whole Biome Study No: WB01-202_Ver 2_Amend 3 06/19/18

Page 10 of 45

I. Inclusion Criteria:

- 1. Age: 18 to 75 years of age
- 2. Have type 2 diabetes treated with diet and exercise alone or in combination with metformin and/or sulfonylurea
- 3. If treated with metformin and/or sulfanylurea, must have been on a stable dose of the drug(s) for a minimum of 3 months with a stable A1c value
- 4. If treated with diet and exercise alone, must have one of the following:
 - a. Documented fasting plasma glucose >126 mg/dL
 - b. A1c value ≥6.8%
- 5. If treated with diet and exercise + metformin and/or sulfonylurea, must have a stable A1c between 6.8% and 11.0% for approximately 3 months
- 6. BMI >25 but <45 and weight stable within +/- 5% over past 3 months
- 7. If female, must meet all the following criteria:
 - a. Not pregnant or breastfeeding

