 - b. If of childbearing potential (including peri-menopausal women who have had a menstrual period within one year) must practice and be willing to continue to practice appropriate birth control (defined as a method which results in a low failure rate, i.e., less than 1% per year, when used consistently and correctly, such as double barrier methods [male condom with spermicide, with or without cervical cap or diaphragm], implants, injectable or oral contraceptives [must have been using for at least the last 3 months], some intrauterine contraceptive devices, tubal ligation, or in an established relationship with a vasectomized partner) during the entire duration of the study
- 8. Have a home freezer available for immediate freezing of stool samples
- Able to read, understand, and sign the informed consent form (ICF) and, when applicable, an authorization to use and disclose protected health information form (consistent with Health Insurance Portability and Accountability Act of 1996 [HIPAA] legislation as modified in 2013)
- 10. Able to communicate with the investigator, and understand and comply with protocol requirements

Whole Biome Study No: WB01-202_Ver 2_Amend 3 06/19/18

Page 11 of 45

J. Exclusion Criteria:

- 1. Subjects who have received an antibiotic, antifungal, antiparasitic, or antiviral treatment within 30 days prior to study entry
- 2. Subjects who plan to use antibiotic, antifungal, antiparasitic, or antiviral treatment during the study
- 3. Subjects using a proton pump inhibitor must be on a stable dose that will be maintained throughout the study period
- 4. Present use of probiotics/nutritional supplements. (Note: The use of replacement doses of Vitamin D, calcium supplements, and a single daily multi-vitamin tablet is allowed)
- 5. Subjects who have participated in a structured weight-loss program within the past 2 months
- 6. Subjects who have changed body weight ≥5% within the past month
- Excess alcohol consumption; with an alcoholic drink defined as 12 fluid ounces of beer (5% alcohol), 5 fluid ounces of wine (12% alcohol) or 1.5 fluid ounces of 80 proof distilled spirits
 - a. Women: More than 2 alcoholic drinks/day or more than 7 drinks/week
 - b. Men: More than 3 alcoholic drinks/day or more than 10 drinks/week
- 8. Subjects who have travelled outside the United States within 30 days prior to study entry
- 9. Subjects who plan to travel outside the United States during the projected study period

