- 10. Subjects who have received an experimental drug within 30 days prior to study entry
- 11. Subjects with known milk, peanut, tree nut, wheat, soy or shellfish allergies
- 12. Subjects who have been diagnosed with a sexually transmitted disease including, but not limited to, HIV, syphilis, herpes, gonorrhea, hepatitis A, hepatitis B, and hepatitis C
- 13. Hospitalization for any reason within the 3 months prior to study entry (Same day surgery center visits/procedures allowed)
- 14. Any active GI disease
- 15. History of any surgery on the gastrointestinal tract except appendectomy and cholecystectomy
- 16. Cystic fibrosis
- 17. Subjects with any condition that the investigator deems as a sound reason for disqualification from enrollment into the study

Whole Biome Study No: WB01-202_Ver 2_Amend 3
06/19/18

K. Removal of Subjects from Study Participation:

 Withdrawal of Consent - Subject wishes to withdraw from the study as outlined in the informed consent form. All subjects reserve the right to withdraw from the study without prejudice to themselves or their future medical care.

- 2. Adverse Event Subject experiences an adverse event, which in the investigator's opinion necessitates withdrawal from the study.
- 3. Investigator Decision Investigator assessment that it is in the subject's best interest to terminate participation.
- 4. Protocol Violation Includes subject non-compliance, documented pregnancy, study entry criteria violation, and/or initiation of an unacceptable concomitant medication, especially antibiotics, unless approved by Sponsor.
- 5. Lost to Follow-Up Subject fails to return for study visits and cannot be reached with reasonable attempts.
- 6. Administrative Reason Includes discontinuation of the study protocol by the sponsor, the Food and Drug Administration (FDA), or other regulatory authority, and/or discontinuation of the study site's participation in the study protocol.

Any withdrawal from the study will be fully documented. The documentation will include reasons for the withdrawal and details of any sequelae (followed through until the symptoms have resolved or returned to baseline levels) if the reason for withdrawal was an adverse event. Whenever possible, subjects terminating early will have the procedures outlined in Visit 7. (Note: If the subject has been receiving Study Product for <4 weeks, the MTT and inflammatory markers should be omitted.)

L. Subject Information and Samples:

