- e. Review of concomitant medications
- f. Blood sample collection for the following assessments:
 - i. HIV, Hepatitis C, Hepatitis B, Hepatitis A serologies
 - ii. Serum pregnancy test
 - iii. Chemistry panel (includes glucose, urea nitrogen, creatinine, total protein, albumin, uric acid, total and fractionated bilirubin, alkaline phosphatase, alanine aminotransferase (ALT), aspartate aminotransferase (AST), gamma glutamyltranspeptidase (GGT), creatine phosphokinase (CPK), sodium, potassium, chloride, bicarbonate, phosphate, calcium, and magnesium)
 - iv. Hematology panel (includes red cell count, hemoglobin, hematocrit, white cell count, platelets, differential count, mean cell volume, mean corpuscular hemoglobin, and mean corpuscular hemoglobin concentration)
 - v. Hemoglobin A1c
- g. Review instructions for stool collection [Appendix 2] and dispense a stool collection kit for collection of a stool sample prior to the baseline visit (Visit 1/Day 0). (Note: Subjects should be instructed to freeze the sample in their home freezer immediately after collection and bring the sample frozen to the clinic at their next visit)

2. Baseline (Visit 1/Day 0)

The following procedures will be completed at Visit 1:

a. Physical examination, including vital signs, weight, BMI, and waist circumference

Whole Biome Study No: WB01-202_Ver 2_Amend 3 06/19/18

Page 16 of 45

- b. Review of concomitant medications
- c. Adverse event review
- d. Delivery of the baseline frozen stool sample to clinic staff
- e. Establish venous access for conduct of the standardized Meal Tolerance Test (MTT) according to the procedures outlined in **Appendix 3** (Blood samples for the measurement of plasma glucose and insulin at T=0, 30, 60, 90, 120, and 180 minutes relative to ingestion of a standardized liquid mixed meal (Boost PlusTM, 475 mL = 720 calories)
- f. Using the established venous access, draw bloods for the following **prior to ingestion of the meal:**
 - (i) Chemistry and hematology panels (Safety labs)
 - (ii) Hemoglobin A1c
 - (iii) Fasting total cholesterol, TGs, LDL, and HDL cholesterol (unless included in chemistry panel)
 - (iv) Inflammatory marker panel (CRP, IL-6, IL-10, TNF- α , and TGF- β)
 - (v) 10 mL of blood for a frozen, stored serum sample for the measurement of other hormones, short chain fatty acids, and other metabolites, should study results warrant
- g. ECG
- h. Urine Analysis
- i. Complete Hospital Anxiety and Depression Scale [Appendix 4] questionnaire

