- RELATED: The adverse event is judged to be related to the administration of study medication.

Q. Blood Volume:

During this study, blood will be drawn for various analytes and panels, including chemistry, hematology, insulin, and inflammatory markers. The total amount of blood to be drawn (during the entire study) is expected to be \sim 120 mL, which is equivalent to 4 ounces, or 0.3 pints for each subject.

R. Data Management:

All data collected will be entered into electronic Case Report Forms (eCRFs) built upon the OpenClinica platform. The eCRFs enter the collected data into a database that will allow summaries and the statistical analyses outlined in the statistical analysis plan to be conducted.

Whole Biome Study No: WB01-202_Ver 2_Amend 3 06/19/18

Page 24 of 45

Upon conclusion of the study, all materials, including a copy of the final, locked electronic database, will be archived.

S. Statistical Considerations:

Analysis Populations:

- Intent-To-Treat (ITT): The ITT Population will include all randomized subjects who receive at least one portion of randomized study product, i.e. Placebo (WBF-0009), WBF-0010, or WBF-0011.
- Evaluable: The evaluable population will include all ITT subjects who have had adequate exposure to the randomized study product during the 12-week treatment period (Day 0/Visit 1 to Week 12/Visit 7) and have adequately complied with the protocol as assessed by the investigator and sponsor prior to database lock. Additional subjects may be excluded from the evaluable population based on a clinical review of the data prior to database lock with the reason(s) for exclusion recorded. The final definition of the evaluable population will be documented in the prospectively developed statistical analysis plan (SAP), which be submitted for IRB review prior to database lock.

Statistical Analyses:

- **Primary Safety and Tolerability Endpoint:** The primary safety and tolerability endpoint is the incidence of all treatment-emergent adverse events.
- **Primary Efficacy Endpoint:** The primary metabolic efficacy endpoint for the study is the change from baseline to Week 12 in the area under the glucose curve (ΔAUCglucose ₍₀₋₁₈₀₎) during a standardized 3-hour meal tolerance test (MTT). The primary inflammation efficacy endpoint for the study is the change from baseline to Week 12 in CRP.

• Secondary Endpoints:

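### The primary CRP change rests on one draw at each end, with no rule for acute illness, injury or vaccination at the time of either draw

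*Protocol*

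**What the plan says.** Section D (Primary Endpoint) states that "the primary inflammatory endpoint is the change from baseline to Week 12 in c-reactive protein (CRP"), and Section S repeats it: "The primary inflammation efficacy endpoint for the study is the change from baseline to Week 12 in CRP". The rationale in Section B is chronic: "Patients with type 2 diabetes exhibit both deranged carbohydrate metabolism and a generalized inflammatory state".

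Sampling is fixed in Sections F and N:
- **Screening:** the listed blood tests do not include CRP.
- **Visit 1 (Day 0) and Visit 7 (Week 12):** one panel each, before the test meal, listed as "Inflammatory marker panel (CRP, IL-6, IL-10, TNF- α , and TGF- β").
- **Week 4:** the note under Figure 1 says that "at Visit 3 (Week 4), only CRP, IL-6, and TNF- α are collected". This CRP value serves a secondary endpoint only.

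Protection against acute or inflammatory states is spread over several places:
- Section J excludes anti-infective treatment in the previous 30 days or planned during the study (items 1 and 2), listed infections (item 12), hospitalization in the previous 3 months (item 13) and "Any active GI disease" (item 14). Item 17 leaves other conditions to the investigator.
- Section K (ground 4) allows removal for starting an unacceptable medication, with antibiotics singled out.
- Section S allows exclusions from the evaluable population after a clinical review before database lock.

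Neither the Visit 1 nor the Visit 7 procedures say what to do with the CRP draw if the subject is acutely unwell, injured or recently vaccinated. The adverse-event review at Visit 7 is non-directed. Section H expects about 20 completers per arm, and Section U gives no power calculation.

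**The concern.** The target is the persistent low-grade inflammation of type 2 diabetes, but CRP also rises briefly with infection, injury or vaccination. A change score built on one value at each end has nothing to average such a rise away. A subject who is ill at Day 0 contributes what looks like a large fall, and one who is ill at Week 12 contributes what looks like a rise.

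The existing criteria act mostly at entry, and mostly on treated infection and GI disease. A mild untreated cold, dental work or a vaccination can pass through at Day 0, and no rule covers them at Week 12. A non-directed adverse-event review may not record them either. A later analysis would then have no dependable marker of which values were affected. Sampling, and what is asked at the visit, are protocol matters that the SAP cannot supply afterwards.

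**Working it through.** The protocol states no effect size, SD or power for CRP, so there is no figure to reproduce. What follows is a sensitivity calculation.

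**From the protocol:** about 60 completers in three arms, 60/3 = 20 per arm. One CRP draw at each end gives 40 draws per arm and 80 for one active arm against placebo.

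**Assumed, not in the protocol:** median CRP 3 mg/L; between-subject log-SD 1.0; within-subject log-SD *s* = 0.4 or 0.6; each draw affected independently with probability *p* = 0.02 or 0.05; an affected draw gains 15–60 mg/L.

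**1. How often.** Expected affected draws = 80*p* = 1.6 to 4. Chance of at least one = 1 − (1 − *p*)^80 = 0.80 at *p* = 0.02 and 0.98 at *p* = 0.05.

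**2. Effect of one spike on a raw mean.** Spike/20: a spike of 30 mg/L moves the arm's mean change by 30/20 = 1.5 mg/L.

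**3. SD of change.** Without spikes, the log-scale SD is *s*√2, so 0.4 × 1.414 = 0.57 and 0.6 × 1.414 = 0.85. Simulation with spikes gives:

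| *s* | Scale | No spikes | *p* = 0.02 | *p* = 0.05 |
|---|---|---|---|---|
| 0.4 | log | 0.57 | 0.78 | 1.01 |
| 0.6 | log | 0.85 | 1.00 | 1.19 |
| 0.4 | mg/L | 5.2 | 9.4 | 13.3 |
| 0.6 | mg/L | 9.1 | 12.0 | 15.3 |

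**4. Loss of information on the log scale.** The variance ratio runs from (1.00/0.85)² ≈ 1.4 to (1.01/0.57)² ≈ 3.1. So 20 completers per arm carry the information of about 20/1.4 ≈ 14 down to 20/3.1 ≈ 6.

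**5. Sign of the estimate.** Assume a true 30% reduction, |ln 0.7| = 0.357. The standard error of the arm difference is SD × √(2/20), and the chance of the wrong sign is Φ(−0.357/SE). This ignores the slight dilution of the effect by spikes.
- *s* = 0.4: SE 0.18 without spikes gives 2%. SE 0.25–0.32 with spikes gives 7–13%.
- *s* = 0.6: SE 0.27 gives 9%. SE 0.32–0.38 gives 13–17%.

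On the raw scale, simulation puts the wrong-sign rate at 28–35% with spikes, against 13–22% without.

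**6. Power and type I error.** For the same 30% reduction, simulated log-scale power falls from about 49% to 33–20% (*s* = 0.4), or from about 25% to 20–16% (*s* = 0.6). With no true effect, the rejection rate stays at or below about 5% on the raw and log scales. A separate simulation with spikes of 10–50 mg/L and rates up to 10% agrees, and its rank test also stays there.

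**7. Averaging two baseline values.** The within-subject variance of change falls from 2*s*² to *s*²/2 + *s*² = 1.5*s*². The SD is then √(1.5/2) = 0.87 of the single-baseline value, before spikes are considered.

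**The case against.** The strongest reply is that the protocol already holds much of what is needed. Visits 1 and 7 list a physical examination with vital signs, a medication review and an adverse-event review ahead of the draw. White cell and differential counts are taken with the CRP. Randomization is on Day 0, so the investigator can use exclusion 17 for anyone visibly ill. The pre-lock review can remove an ill subject from the evaluable population. Week 4 CRP and the other markers offer a cross-check. The study is exploratory, and every figure on size above is assumed. All of this stands, and it lowers the priority. It does not supply a rule for the draw, a look-back for events such as vaccination or dental work, or an illness flag for the ITT analysis.

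A reader might also infer more than the documents support:
- **That acute or inflammatory states are not kept out at all.** The exclusions, the removal ground and the pre-lock review give real, if partial, cover. The protocol is silent on an ill subject at the draw; it does not order the draw regardless.
- **That a few spikes could settle the result or manufacture an effect.** Under blinded random allocation they fall on the arms by chance, and the false-positive rate does not rise.
- **That uncontrolled non-GI inflammatory disease or anti-inflammatory treatment undermines the endpoint.** No criterion names them, but stable disease and stable treatment largely cancel in a change score and are balanced in expectation by randomization. Nothing here quantifies a residual effect, and concomitant-treatment rules are not proposed.
- **That a missing transformation or outlier rule is a fault.** These may be in the SAP, which is not shown.

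**Conclusion.** The point holds as a limited design weakness. A named primary endpoint depends on one CRP value at each end, and no rule deals with acute illness, injury or vaccination when those values are drawn. The consequence is lost precision and an unstable sign, with type I error unaffected. Under the assumed inputs, the variance of log change is about 1.4 to 3.1 times its spike-free value. The low end needs only 2% of draws affected and a noisy marker; the high end needs 5% and a steadier one. If acute events at the draws are rarer than 2%, the loss is smaller. A log-scale or rank analysis reduces the loss but does not remove it. Because the study is exploratory and partial safeguards exist, this is a cheap improvement worth making, not an obstacle to running the trial.

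**What to change.** 1. At Visits 1 and 7, before the CRP draw, ask a structured question on infection, injury, dental work or vaccination in the past 2 weeks, and record the answer in the eCRF.
2. If positive at Visit 1, defer Day 0. This must be reconciled with the screening window of Day −14 to Day −7. For example, a subject screened 10 days before the visit and vaccinated 3 days before it needs 11 more days to clear the look-back, so Day 0 would fall 10 + 11 = 21 days after screening. The protocol should say whether the window extends or screening is repeated.
3. If positive at Visit 7, keep the value in the ITT analysis, flag it, and prespecify a sensitivity analysis without flagged values.
4. Optionally, assay CRP on the blood already drawn at screening and use the mean of the two pre-product values as baseline. This brings the SD of change to about 0.87 of its single-baseline value, but leaves half of a spike at either baseline draw and does nothing at Week 12.

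Cost: a protocol amendment, one eCRF item at two visits, a few postponed baselines and, if item 4 is adopted, one extra assay per screened subject.
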